### 8.1.1 Screening

Screening Visit assessments are listed in [Table 3-1](#).

Screening will occur within 28 days before administration of LUM/IVA. The investigator (or an appropriate authorized designee at the study site) will obtain informed consent or assent from each subject. If the time between screening and dosing exceeds 28 days as a result of unexpected operational delays (e.g., delayed drug shipment), then subjects do not require rescreening.

To prepare for study participation, subjects will be instructed on the study restrictions ([Section 9.3](#)).

Subjects previously screened for another Vertex study may participate in this study if they meet the eligibility criteria. Screening data from the previous study may be used for this study if they were obtained within 28 days before administration of LUM/IVA.

Subjects who do not meet the eligibility criteria may not be rescreened, with the following exceptions, all of which require medical monitor approval:

- Subjects who met all eligibility criteria but had an intercurrent illness (e.g., upper respiratory infection with fever) in the 5 days before the first LUM/IVA dose that was properly evaluated and which resolved fully
- Subjects who met all eligibility criteria but are not able to obtain required documentation within the allotted screening window
- Subjects who met all eligibility criteria but transiently (for personal reasons) are unable to commit to all study procedures
- Subjects who met all eligibility criteria but are not randomized for administrative reasons (e.g., interactive web response system is temporarily inaccessible or nonfunctional or LUM/IVA is not available at the study site)

Any subject granted approval by the medical monitor for any of the exceptions listed above may have the screening window extended by 1 week before needing to undergo any rescreening assessments. If more than 35 days have elapsed from screening before first dose of LUM/IVA, all screening assessments need to be repeated. Repetition of any screening assessment that did not meet eligibility criteria is not permitted, unless there is clear evidence of a laboratory error (e.g., hemolysis of sample). In all cases, the medical monitor must authorize retesting.

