## 9.2 Exclusion Criteria

Subjects who meet any of the following exclusion criteria will **not** be eligible.

1. History of any illness or any clinical condition that, in the opinion of the investigator, might confound the results of the study or pose an additional risk in administering LUM/IVA to the subject, e.g., history of advanced liver disease.
2. Presence of moderate or severe hepatic impairment (Child-Pugh Class B or C).
3. Subjects currently receiving invasive mechanical ventilation.
4. Known history of alcohol or drug abuse in the past year, including but not limited to cannabis, cocaine, and opiates, as deemed by the investigator.
5. Any of the following abnormal laboratory values during screening:
  - o Alanine aminotransferase (ALT) or aspartate aminotransferase (AST)  $>5 \times \text{ULN}$
  - o ALT or AST  $>3 \times \text{ULN}$  with total bilirubin  $>2 \times \text{ULN}$
  - o Glomerular filtration rate  $\leq 30 \text{ mL/min/1.73 m}^2$ . This will be calculated by the Modification of Diet in Renal Disease study equation for subjects  $\geq 18$  years of age and calculated by the Counahan-Barratt equation for subjects aged 12 to 17 years.
6. Pregnant or nursing females (females of childbearing potential must have a negative pregnancy test at screening and Day 1).
7. Female subjects and female partners of male subjects who plan to become pregnant during Treatment Period or within 90 days following the last dose of LUM/IVA.
8. Sexually active subjects of reproductive potential who are not willing to follow the contraception requirements outlined in Section 11.5.7.1.
9. History of solid organ or hematological transplantation.
10. Ongoing or prior participation in an investigational drug study (including studies investigating LUM and/or IVA) within 30 days of screening
  - A washout period of 5 terminal half-lives of the previous investigational LUM/IVA or 30 days, whichever is longer
  - The duration of the elapsed time may be longer if required by local regulations.
11. Current use of commercial LUM/IVA combination therapy.

12. Subject, or close relative of the subject, is the investigator or a subinvestigator, research assistant, pharmacist, study coordinator, or other staff directly involved with the conduct of the study at that site.

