### **9.3 Study Restrictions**

#### **9.3.1 Prior and Concomitant Medications and Other Study Restrictions**

Information regarding all prior and concomitant medications, including the subject's CF medications, other medications, and herbal and naturopathic remedies administered from 30 days before the Screening Period through the Safety Follow-up Visit will be recorded in each subject's source documents and electronic case report form (eCRF). For subjects who are screened but are not enrolled in the study, details of prior medications will be documented only in the subjects' source documents.

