##### **9.3.1.1 Drug Interactions**

A nonexhaustive list of established and potentially significant drug interactions, including information on dosage adjustment, is provided in the approved product label for LUM/IVA (Orkambi®) (see study reference manual).

LUM is a strong inducer of CYP3A. Administration of LUM/IVA may decrease systemic exposure of medicinal products that are substrates of CYP3A, which may decrease therapeutic effect. Coadministration with sensitive CYP3A substrates or CYP3A substrates with a narrow therapeutic index is not recommended.

IVA is a substrate of CYP3A4 and CYP3A5 isoenzymes. Use of LUM/IVA with strong CYP3A inducers significantly reduces IVA exposure, which may reduce the therapeutic effectiveness of LUM/IVA. Therefore, coadministration with strong CYP3A inducers (e.g., rifampicin, St. John's wort [*Hypericum perforatum*]) is not recommended.

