### 12.3.5.1 Adverse Events

For analysis purposes, AEs will be classified as pretreatment AEs, TEAEs, or post-treatment AEs, defined as follows:

- **Pretreatment AE:** any AE that started before the first dose of LUM/IVA
- **TEAE:** any AE that increased in severity or that was newly developed at or after the first dose of LUM/IVA to 28 days after the last dose of LUM/IVA
- **Post-treatment AE:** any AE that increased in severity or that was newly developed after 28 days after the last dose of LUM/IVA

For AEs with missing or partial start dates, if there is no clear evidence that the AEs started before or after study treatment, then the AEs will be classified as TEAEs.

AE summary tables will be presented for TEAEs only and will include the following:

- All TEAEs
- TEAEs by relationship
- TEAEs by maximal severity
- TEAEs leading to treatment discontinuation
- Serious TEAEs
- TEAEs leading to death

Summaries will be presented by MedDRA System Organ Class and preferred term using frequency counts and percentages by study arm (i.e., number and percentage of subjects with an event as well as total number of events). When summarizing the number and percentage of subjects with an event, subjects with multiple occurrences of the same AE or a continuing AE will be counted once; only the maximum severity level will be presented in the severity summaries and the worst/highest relationship level presented in the relationship summaries. In addition, summary tables containing individual subject AE data for all deaths and other serious and significant AEs will be provided separately. All AEs, including pre- and post-treatment AEs, will be presented in individual subject data listings.

AEs leading to death, SAEs, dose interruption, and permanent discontinuation will be listed separately. All AEs through the Safety Follow-up Visit will be listed in an individual subject data listing, including pre-treatment AEs.

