### **13.1.1.3 Documentation of Adverse Events**

All AEs will be collected from the time the ICF is signed until the following time points:

- For subjects who do not enroll: until time of screen failure (e.g., screen failure, withdrawal of consent)
- For enrolled subjects who have a Safety Follow-up Visit: through the Safety Follow-up Visit
- For enrolled subjects who do not have a Safety Follow-up Visit, the **earliest** of:
  - 28 days after the last dose of LUM/IVA or
  - Dosing with commercial LUM/IVA

All subjects will be queried, using non-leading questions, about the occurrence of AEs at each study visit. When possible, a constellation of signs and/or symptoms will be identified as 1 overall event or diagnosis. All AEs for enrolled subjects will be recorded in the eCRF and source document. AEs for subjects who are screened but not subsequently enrolled in the study will be recorded only in the subject's source documents. The following data will be documented for each AE:

- Description of the event
- Classification of “serious” or “nonserious”
- Date of first occurrence and date of resolution (if applicable)
- Severity
- Causal relationship to LUM/IVA(s)
- Action taken
- Outcome
- Concomitant medication or other treatment given

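### Exclusion criterion 10 covers any investigational drug study, but its five-half-life washout is worded, probably by a drafting slip, for LUM/IVA only

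*Protocol*

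**What the plan says.** Criterion 10 in Protocol Section 9.2 has a parent sentence and two bullets.

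- The parent sentence sets the scope: "Ongoing or prior participation in an investigational drug study (including studies investigating LUM and/or IVA) within 30 days of screening". Studies of LUM or IVA are an included example, not the limit.
- The first bullet sets the washout: "A washout period of 5 terminal half-lives of the previous investigational LUM/IVA or 30 days, whichever is longer".
- The second allows an extension: "The duration of the elapsed time may be longer if required by local regulations".

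Two timing rules bear on the point. Section 8.1.1 states that "Screening will occur within 28 days before administration of LUM/IVA". Section 8.1.3 places this study's own Safety Follow-up Visit 28 (±7) days after the last dose.

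**The concern.** The exclusion is broad, but the bullet that lengthens it names one product. An earlier investigational agent other than LUM/IVA falls under the parent sentence but not, on its literal words, under the half-life rule. For such an agent only the 30 days remain, plus whatever local regulations add.

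This is an operative eligibility rule, and SAP Section 8.2.7 lists entry in violation of an exclusion criterion as a potential important protocol deviation. Two sites could therefore classify the same candidate differently, each with a defensible reading.

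What is at stake is residual drug at the first LUM/IVA dose. It matters in two situations. The first is an earlier agent that is a strong CYP3A inducer: Protocol Section 9.3.1.1 says "Use of LUM/IVA with strong CYP3A inducers significantly reduces IVA exposure, which may reduce the therapeutic effectiveness of LUM/IVA". The second is adverse-event attribution. Section 12.3.5.1 counts as treatment-emergent any event "newly developed at or after the first dose of LUM/IVA to 28 days after the last dose of LUM/IVA", so an event due to the earlier drug could enter those tables, and the causality judgement in Section 13.1.1.5 becomes harder.

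**Working it through.** **Does another rule close the gap?**

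- Criterion 1 concerns illness or clinical condition and sets no washout.
- Criterion 11 concerns current commercial LUM/IVA only.
- Section 9.3.1 requires that medications "administered from 30 days before the Screening Period through the Safety Follow-up Visit will be recorded". That is a recording rule, not an eligibility check.
- Section 9.3.1.1 advises against coadministration with strong CYP3A inducers but sets no washout for an earlier investigational agent.
- The SAP contains no eligibility criteria.

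No other rule supplies a half-life washout for other agents.

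**When do 30 days fall short?** The plan gives no figure to reproduce. The inputs are 5 half-lives and 30 days (criterion 10). I assume that the washout is measured to screening, as in the parent sentence.

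5 × t½ > 30 days when t½ > 30/5 = 6 days.

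**Shortest permitted gap to first dose.** Take a subject screened exactly 30 days after leaving the earlier study and dosed 1 to 28 days later (Screening Period Day -28 to Day -1). The documents do not say how long the earlier study followed subjects after their last dose, so I show two assumptions. The second borrows the 28 (±7) days that this protocol sets for itself.

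| Assumed earlier follow-up | Gap, last earlier dose to first LUM/IVA dose | Half-life threshold = gap/5 |
|---|---|---|
| None | 30+1 = 31 to 30+28 = 58 days | 6.2 to 11.6 days |
| 28 (±7) days | 30+21+1 = 52 to 30+35+28 = 93 days | 10.4 to 18.6 days |

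Five half-lives are incomplete at first dose only for a half-life above the threshold.

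**Residual drug at those gaps.** With first-order elimination, the fraction left is 2^(−gap/t½). After five half-lives it is 2^(−5) = 3.1%. The documents give no half-lives, so the values below are illustrative.

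| t½ | 31 days | 58 days | 52 days | 93 days |
|---|---|---|---|---|
| 10 days | 11.7% | 1.8% | 2.7% | 0.2% |
| 15 days | 23.9% | 6.9% | 9.0% | 1.4% |
| 20 days | 34.2% | 13.4% | 16.5% | 4.0% |

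The first two columns assume no earlier follow-up, the last two 21 and 35 days of it. Every entry is a boundary case: criterion 10 sets no maximum gap, and a subject screened later than day 30 has less drug left. Section 8.1.1 also lets screening run past 28 days in some circumstances, which lengthens the gap further.

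**The case against.** The strongest reply is that this is an editorial slip with no practical consequence. The bullet sits under a sentence about any investigational study, so a reader would naturally take it to mean that earlier study's drug. The protocol shows other traces of a global replacement: Section 13.1.1.3 leaves a bracketed plural ending after LUM/IVA, and the resumption text in Section 11.5.3 has a truncated LUM/ with nothing after the slash. Even on the literal reading, any participation within 30 days of screening excludes a subject, local rules may add time, and strong CYP3A inducers are already advised against. Harm would need a literal-minded site, a long half-life agent, enrolment near the minimum gap, and an agent that interacts or clouds causality.

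Most of this stands. It settles that the fault is one of drafting, and it keeps the weight low. It does not make the literal text correct: eligibility is decided on the written criterion, and the safeguards cited are not a half-life washout.

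Three stronger inferences are tempting, and the documents support none of them.

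- *The sponsor chose a shorter washout for other agents.* Nothing in the rationale sections suggests such a choice, and the drafting traces point the other way.
- *Subjects entered with a third of an earlier drug still on board.* The 34.2% figure needs an assumed 20-day half-life, no earlier follow-up, screening on the boundary and dosing the next day. The documents name no such agent.
- *The 30-day medication record would hide such subjects.* Criterion 10 itself obliges the site to establish prior study participation, and Section 9 requires eligibility to be reviewed and documented before enrolment.

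**Conclusion.** The point holds as a drafting error in an operative rule, of minor weight. On its literal words, criterion 10 applies the half-life washout to earlier investigational LUM/IVA only. Other agents can clear it with fewer than five half-lives elapsed at screening if their half-life exceeds 6 days. By first dose, at the minimum permitted gap, the threshold is 6.2 to 11.6 days with no earlier follow-up and 10.4 to 18.6 days with 28 (±7) days of it. These figures rest on first-order elimination, on screening at the 30-day boundary and on the assumed follow-up. The number of subjects affected is unknown and probably very small, possibly none.

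A reader might infer that the gap could bias the trial's main result. It does not. Both arms take the same LUM/IVA regimen and adherence is counted from bottle openings, so the comparison between arms, the power and the alpha are unaffected. Safety analysis is descriptive only (SAP Section 8.4). SAP Section 3 reports that the study was terminated early, so the correction now matters mainly if the criterion is reused.

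**What to change.** In the first bullet of criterion 10, replace *LUM/IVA* with *drug*, so that the washout refers to the previous investigational drug and covers everything in the parent sentence. Keep the five half-lives or 30 days, whichever is longer, and keep the local-regulation line.

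Nothing changes for half-lives up to 6 days. The cost is a longer wait before screening for a rare candidate coming off a long half-life agent:

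- **No earlier follow-up:** the extra wait is max(0, 5 × t½ − 30). A 10-day half-life means 50 days instead of 30 (20 more), and a 20-day half-life means 100 instead of 30 (70 more).
- **28 (±7) days of earlier follow-up:** 51 to 65 days have already passed at the 30-day point. The extra wait is 0 days for a 10-day half-life, and 100 − 65 = 35 to 100 − 51 = 49 days for a 20-day half-life.

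No sample-size, analysis or SAP change is needed.

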### **9.3 Study Restrictions**

#### **9.3.1 Prior and Concomitant Medications and Other Study Restrictions**

Information regarding all prior and concomitant medications, including the subject's CF medications, other medications, and herbal and naturopathic remedies administered from 30 days before the Screening Period through the Safety Follow-up Visit will be recorded in each subject's source documents and electronic case report form (eCRF). For subjects who are screened but are not enrolled in the study, details of prior medications will be documented only in the subjects' source documents.

##### **9.3.1.1 Drug Interactions**

A nonexhaustive list of established and potentially significant drug interactions, including information on dosage adjustment, is provided in the approved product label for LUM/IVA (Orkambi®) (see study reference manual).

LUM is a strong inducer of CYP3A. Administration of LUM/IVA may decrease systemic exposure of medicinal products that are substrates of CYP3A, which may decrease therapeutic effect. Coadministration with sensitive CYP3A substrates or CYP3A substrates with a narrow therapeutic index is not recommended.

IVA is a substrate of CYP3A4 and CYP3A5 isoenzymes. Use of LUM/IVA with strong CYP3A inducers significantly reduces IVA exposure, which may reduce the therapeutic effectiveness of LUM/IVA. Therefore, coadministration with strong CYP3A inducers (e.g., rifampicin, St. John's wort [*Hypericum perforatum*]) is not recommended.

### **9.4 Removal of Subjects**

Subjects may withdraw from the study at any time at their own request and subjects may be withdrawn at any time at the discretion of the treating physician or by Vertex for safety, behavior, noncompliance with study procedures, or administrative reasons. LUM/IVA treatment will be withdrawn for any female subject who has confirmed pregnancy and for any male subject whose female partner has a confirmed pregnancy. A subject may be withdrawn from the LUM/IVA treatment after a discussion between the investigator and the medical monitor for any of the following reasons:

- A subject develops a medical condition that requires prolonged concomitant therapy with a prohibited medication or prolonged interruption of LUM/IVA combination therapy.
- A subject develops a life-threatening adverse event or a serious adverse event (SAE) that places him/her at immediate risk, and discontinuation of treatment with LUM/IVA and withdrawal from the study are deemed necessary
- A subject is noncompliant with the study requirements
- A subject has an increase in transaminases (ALT or AST), meeting criteria for interruption of LUM/IVA in Section 11.5.3.

A subject should be discontinued from the study for the following reason:

A subject on a transplant list undergoes lung transplantation

If a subject does not return for a scheduled visit, reasonable effort will be made to contact the subject. In any circumstance, reasonable effort will be made to document subject outcome. The investigator will inquire about the reason for withdrawal, request that the subject return all unused LUM/IVA, request that the subject return for a Safety Follow-up Visit, if applicable (see Section 8.1.4), and follow up with the subject regarding any unresolved AEs.

If the subject withdraws consent for the study, no further evaluations will be performed and no additional data will be collected. Vertex may retain and continue to use any data collected before such withdrawal of consent.

## **9.5 Replacement of Subjects**

Subjects who withdraw or are withdrawn for nonsafety reasons during the LUM/IVA treatment period(s) may be replaced at Vertex's discretion.

# **10 STUDY DRUG AND SMART ADHERENCE TECHNOLOGIES ADMINISTRATION AND MANAGEMENT**

## **10.1 Preparation and Dispensing**

### **10.1.1 LUM/IVA**

LUM/IVA may be dispensed only under the supervision of the investigator or an authorized designee and only for administration to the study subjects.

Blister pack tablets will be dispensed at the CRU into individual smart pill bottles by 2 operators, 1 of whom is a qualified pharmacist, and following national and local laws and regulations.

### **10.1.2 Smart Adherence Technologies**

[Table 8-1](#) describes the smart adherence technologies used in this study. Site pharmacists will distribute the assigned smart adherence technology to each subject with LUM/IVA.

#### Smart Pill Bottles

Subjects will be trained to use the smart pill bottle. Subjects in Study Arm A will receive additional instruction on the activated smart pill bottle monitoring features. A site pharmacist will repackage 3 months supply of LUM/IVA from blister packs into 4 Smart Pill Bottles. Three bottles will each store a 1-month supply of LUM/IVA. A fourth bottle will store an additional 7 days supply of LUM/IVA. Only 1 bottle will be activated at a time.

## **10.2 Administration**

### **10.2.1 LUM/IVA**

LUM/IVA fixed-dose tablet will be administered orally ([Table 10-1](#)).

**Table 10-1 LUM/IVA Administration**

All Subjects	Time	LUM/IVA (200/125 mg per tablet)
LUM 400 mg/IVA 250 mg q12h	AM	2 tablets
	PM	2 tablets

IVA: ivacaftor; LUM: lumacaftor; q12h: every 12 hours

LUM/IVA should be administered within 30 minutes of consuming fat-containing food such as a standard CF high-fat, high-calorie meal or snack. LUM/IVA should be administered q12h ( $\pm$  4 hours).

### **10.3 Method of Assigning Subjects to Treatment Groups**

Approximately 75 subjects who meet the eligibility criteria will be randomized at 2:1 ratio to 1 of 2 study arms. All subjects will receive LUM/IVA. Subjects will be stratified by age ( $<23$  versus  $\geq 23$  years of age) and FEV1 severity ( $<70\%$  versus  $\geq 70\%$  predicted) determined at the Screening Visit.

An interactive web response system (IWRS) will be used to assign subjects to study arms. Detailed instructions for randomization will be provided separately.

### **10.4 Dose Modification for Toxicity**

If any unacceptable toxicity arises, a dose modification to LUM 200 mg/IVA 125 mg q12h for up to 7 days may be permitted after discussion with and approval by the medical monitor. Subjects who receive the LUM/IVA dose modification will be administered 1 tablet in the morning and 1 tablet in the afternoon and follow administration instructions as described in Section 10.2.

The medical monitor should be contacted before transitioning subjects back to LUM 400 mg/IVA 250 mg q12h.

